7.2 Exclusion Criteria

1. Subject has been administered any other radiopharmaceutical within a timeframe that might cause interference with study imaging.
2. Subject is a pregnant or lactating female.
3. Subject has received Technegas in the past.
4. Subject has received an investigational drug within 30 days prior to dosing.
5. Subject is hemodynamically unstable.

7.3 Withdrawal or Termination of Participation

Every subject has the right to terminate his or her participation in the study at any time without providing reasons. A subject's participation will terminate immediately upon his/her request.

A subject who signs the informed consent form, but discontinues study participation without inhaling Technegas is termed a withdrawn subject. Subjects may withdraw themselves or may be withdrawn by the investigator. Data collection for withdrawn subjects will cease at the time of their withdrawal.

Subjects may withdraw or be withdrawn for any of the reasons listed below:

- Did not meet inclusion/exclusion criteria
- Withdrew consent
- Lack of compliance with study procedures
- Investigator decided it is in the subject's best interest to be withdrawn

A subject who signs the informed consent form and then undergoes Technegas inhalation, but does not complete all of the imaging procedures and/or all of the safety assessments including clinical laboratory evaluation, is termed an **incomplete subject**.

Whatever the reason for lack of study completion, the investigator should attempt to collect and report the required Technegas safety data.

A subject who meets all inclusion criteria and no exclusion criteria, undergoes Technegas inhalation and completes all study procedures is termed a **complete subject**.

8 Treatment of Subjects

Subjects will undergo Xe-133 and Technegas inhalation and imaging. Safety will be monitored pre- and post-inhalation of Technegas by assessing changes in clinical laboratory measurements, vital signs, blood oxygen saturation by pulse oximetry, and physical examination.

Subjects must agree to return for an in-person 24-hour follow-up after Technegas inhalation to obtain safety assessments. Prior to enrolling the subject, the required 24-hour follow-up safety assessment will be discussed with the patient and documented. Subjects that agree to return for the 24-hour follow-up and sign the informed consent form will be entered into the study.

If a subject withdraws consent for participation by not returning for the 24-hour follow-up safety assessment, the subject will be considered to be an incomplete subject. However, the subject must be contacted by telephone, interviewed for treatment emergent adverse events and the contact must be documented in the subject's source records. All attempts to reach the subject by telephone, or by mail or email if telephone communication cannot be established, must be documented in the subject's source records.

8.1 Treatment Administered

8.1.1 Technegas

Technegas will be manufactured at point of use immediately before administration using the TechnegasPlus Generator.

Subjects will inhale approximately 1.1 mCi (40 MBq) of Technegas for image acquisition.

8.1.1.1 TechnegasPlus Generator

The TechnegasPlus Generator is a microprocessor-controlled device consisting of a 6-liter shielded, sealed generation chamber. The chamber is housed above two (2) electrodes between which a carbon crucible is inserted. A drawer in the front of the generator provides access to the electrodes.

Technegas is produced by vaporization in the generation chamber. The TechnegasPlus Generator includes several automatic security features that allow safe and efficient generation and delivery of the Technegas.

The 6-minute purge phase with argon gas before each generation assures the elimination of air from the sealed chamber. In addition, for each Technegas generation, an automatic leak test is performed during this purge stage.

To assure an accurately reproducible yield and quality of Technegas, a phototransistor is used to monitor and maintain crucible burn temperature of around $2750^{\circ}\text{C} \pm 50^{\circ}\text{C}$ over a 15-second interval. If the acceptable temperature cannot be maintained over a prescribed period, then the TechnegasPlus Generator prohibits the delivery of Technegas to the subject. If the acceptable temperature is maintained over a shorter defined burn period, then the user is notified that the yield could be low. The user then has the option to administer the product to the subject. For the purposes of this protocol, burns that produce a low yield will not be given to study subjects.

Technegas is intended to be administered to the subject within 10 minutes after its generation. After this time, the generator stops delivery to the subject in order to prevent accidental use of expired Technegas.

See the TechnegasPlus Generator User Manual (supplied separately) for complete details and instructions.¹⁰

8.1.1.2 Investigational Agent Preparation

A carbon crucible, pre-moistened with ethanol to assist in the complete loading of the crucible's reservoir, is fitted between electrodes and loaded with the required activity of Tc-99m sodium pertechnetate in approximately 0.14 mL saline (standard Mo-99/Tc-99m generator eluate). The volume and loading time should be recorded on the CRF. Any additional Tc-99m sodium pertechnetate added to the crucible should be recorded as well. The chamber is closed for the evaporation cycle during which a small electric current is used to heat the crucible to approximately 70°C . High-purity argon gas is also passed over the crucible and purges the generation chamber of air and moisture.

The eluate must evaporate to dryness and leave a white crust of salt (sodium chloride and Tc-99m sodium pertechnetate) on the carbon crucible. Technegas is then generated in a short heating cycle where a large electric current is used to rapidly heat the carbon crucible to a temperature of $2750^{\circ}\text{C} \pm 50^{\circ}\text{C}$ for 15 seconds, in an atmosphere of high-purity argon.

The resulting vapor and argon mixture is inhaled by the subject through a disposable PAS, which is a mouthpiece valve-filter transfer tubing assembly. Residual, unused Technegas is purged from the generation chamber with high-purity argon into an exhaust-trapping filter before the chamber can be opened and reloaded for the next cycle.

As the carbon crucibles are intended for single-use, the machine automatically breaks the crucible to prevent accidental re-use. The debris is collected in a tray beneath the electrodes.

8.1.1.3 Argon Gas Source

Argon gas will be supplied by a qualified vendor in stand-alone cylinders and will be

medical-grade high-purity 99.99% argon. Documentation of the batch and cylinder tracking information will be maintained at all sites.

8.1.1.4 Source of Tc-99m Sodium Pertechnetate

All Tc-99m sodium pertechnetate will be obtained from Mo-99/Tc-99m generators approved by state or national regulatory authorities in their respective regions or from local radiopharmacies. Documentation for Technetium received from a local radiopharmacy, such as prescription, radiopharmacy log, delivery receipt, etc, as applicable for a site, will be kept at the site.

8.1.2 Xe-133 Preparation

Xenon Xe-133 gas will be prepared and administered according to the investigational site's standard practice for subjects presenting for ventilation imaging. The radioactivity at time of loading and the start and stop times of inhalation will be captured in the CRF.

8.2 Concomitant Medication

Concomitant medications are any medications, including over-the-counter preparations, which the subject receives within 24 hours prior to signing informed consent through 24-hour follow-up, 20 to 36 hours after Technegas administration. If a Tc-99m MAA perfusion study occurs following Technegas imaging but within this time period, the MAA and radioactive dose associated with the study should be considered a concomitant medication.

All medications given until the 24-hour follow-up safety assessment will be recorded on the CRF. Documentation will include information concerning generic or trade names, indication, total daily dose (including units), route of administration, date of administration, and date of termination. All medications and therapies will be coded using WHODRUG®.

8.3 Subject Compliance

Subjects will be monitored by clinical personnel during each visit of this study. Subjects who are not compliant with the procedures outlined in this protocol should be withdrawn from the study at the discretion of the investigator or the Sponsor.

8.4 Protocol Deviations

An investigator may not deviate from the protocol, except when necessary to eliminate an immediate hazard (risk) to the rights, safety or welfare of a subject. The investigator must notify the sponsor immediately and not enroll any additional subjects or administer the

investigational drug to any subsequent subjects until the immediate hazard is eliminated from the study protocol or otherwise resolved. The investigator must notify the sponsor of all protocol deviations and must notify the IRB/IEC of any protocol deviations following the IRB/IEC standard procedures.

9 Imaging

The same camera should be used to obtain planar Xe-133 and planar Technegas images. Planar scintigraphy with a nuclear medicine gamma camera will be used to image the distribution of both Xe-133 and Technegas. Imaging will first be performed with Xe-133 followed by Technegas. Because of the rapid clearance of Xe-133 from the lungs and the low, non-interfering energy of Xe-133 photons, a washout period is not required.

9.1 Xe-133 Ventilation and Imaging

Xe-133 ventilation and imaging should be performed in accordance with the standard of care for Xe-133 administration and imaging at the investigational site, which will be documented at the Site Qualification visit. Images should be labeled to indicate when each phase of the study begins (first breath, wash-in, wash-out). The wash-in/wash-out protocol for Xe-133 ventilation imaging used at each investigational site will be documented in the study files.

9.2 Technegas Ventilation and Imaging

Technegas inhalation will be performed after the Xe-133 portion of this study. Because of the rapid clearance of Xe-133 from the lungs and the low, non-interfering energy of Xe-133 photons, a washout period is not required. Technegas is administered by inhalation through the PAS within 10 minutes after preparation. This consists of a plastic tube connected to the TechnegasPlus Generator, fitted with a mouthpiece, one-way flow valves and expiration filter.

The subject will be instructed to breathe through the mouthpiece in one of the methods described below:

- Slow, deep breathing from the residual functional capacity (end of calm expiration) followed by a 5-second breath-hold (recommended method)
- Normal breathing with deep inhalations without breath-holding
- Rapid and deep inspirations from the residual functional capacity followed by a breath-hold of about 5 seconds at the end of the inspiration

The count rate should be monitored until a rate of 1.5-2.5 kcps is achieved. This typically requires 1 to 5 breaths, but additional breaths may be necessary to achieve this target. The number of inhalations required to achieve the target counting rate should be recorded on the CRF, along with the time of the first inhalation and time of the final inhalation. To yield uniform apex-to-base deposition, it is recommended that the subject is ventilated in the supine position on the scanning bed with a detector positioned under the bed to monitor the lung count rate.

The same dual-headed camera used for Xe-133 imaging will be used to collect Technegas images in multiple projections.

Technegas images will include a six view image set:

- anterior view
- posterior view
- left posterior oblique view
- right posterior oblique view
- left anterior oblique view
- right anterior oblique view

Additional details and specifications related to the Technegas ventilation and imaging are provided in the Imaging Manual.

10 Assessment of Efficacy

Primary assessments of efficacy will be based on three blinded readers' independent assessments of the Technegas and Xe-133 ventilation images in independent, randomized reading sessions. Readers will be selected as having experience reading both Xe-133 and DTPA ventilation scans. Readers will also receive training on reading Technegas ventilation images.

In each reading session readers will be blinded to all clinical information except the chest X-rays required for this study. At the start of each case read, with the aid of the subject's chest X-ray, a reader will visually divide each lung into three regions of approximately equal size arranged craniocaudally and designated as the right apical, left apical, right mid, left mid, right basal and left basal regions. The readers will then assess each lung region for ventilation, assigning the region a ventilation score on a three-point scale:

- 0 = absent ventilation
- 1 = decreased ventilation
- 2 = normal ventilation.

If a lung region is completely obscured (as a result of pleural effusion for example), or if a lung region is completely absent as a result of lung resection, the region will be designated a score of 99 to indicate that ventilation cannot be assessed.

10.1 Blinded Read of Xe-133 Images

The Xe-133 planar ventilation images will be read by three (3) expert readers, blinded to all clinical information except the chest X-rays required for this study. Each reader will independently assess the images identified only by a random code number, which will dictate the order of presentation of images to the readers. Together with a subject's chest X-ray, a reader will be presented with all acquired ventilation image views for a subject. The reader will visually divide each lung into three regions of approximately equal size as described above and will assign a single ventilation score to each lung region.

Additional details on the blinded read are provided in the CYC-009 Imaging Charter.

10.2 Blinded Read of Technegas Images

In separate reading sessions, the same three readers who assessed the Xe-133 ventilation images will also assess the Technegas planar ventilation images. Again, the readers will be blinded to all clinical information except chest X-rays and the Technegas images will be identified by a random code number, distinct from the Xe-133 assigned code number. Each reader will independently assess the images presented in the order of their assigned code numbers.

Two sequential reads will be conducted of Technegas ventilation images. In the first read of a case, a reader will be presented with the subject's chest X-ray and the subset of ventilation image views that match the views acquired with Xe-133 for that subject. The reader will visually divide each lung into three regions of approximately equal size as described above and then will assign ventilation scores to each lung region based on those views. He/she will then be presented with the additional Technegas image views and will assign a second score based on the complete set of Technegas images for the subject. If the second ventilation score for a region differs from the first, the reader will be asked to document the basis for the changed score.

The ventilation scores obtained from the first Technegas read of the subset of image views that match the Xe-133 image views will be used to determine agreement with Xe-133 for the primary efficacy endpoint. The ventilation scores obtained from the read of all Technegas image views will provide a secondary efficacy endpoint of agreement with Xe-133.

Additional details on the blinded read are provided in the Imaging Charter.

11 Assessment of Safety

Subjects will be screened prior to enrollment in the clinical trial to ensure that they meet all eligibility criteria, which are designed to exclude subjects for whom participation may not be safe. Women who are of childbearing potential must have a negative pregnancy test as part of the eligibility assessments.

11.1 Screening/Baseline Assessments

1. Subject is evaluated against the inclusion/exclusion criteria.
2. If subject meets inclusion/exclusion criteria and agrees to return for 24-hour follow-up, informed consent will be obtained and a subject number will be assigned.
3. Demographic data is obtained (date of birth, gender, and ethnicity).
4. Allergies (including known food, environmental, and drug allergies) are documented.
5. Medical and surgical history is obtained including concomitant medications, smoking history and reason for Xe-133 ventilation imaging.

The following clinical and laboratory studies will be obtained at screening and must be performed within 24 hours prior to the first imaging study:

1. Physical examination including auscultation of the lungs and heart, and height and weight
2. Chest X-ray in either anteroposterior view or posteroanterior view. A chest X-ray obtained within 24 hours of signing the Informed Consent may be used in subjects with no significant clinical change.
3. Clinical chemistry and hematology
4. Serum or urine pregnancy test (for females of childbearing potential)

11.2 Safety Indicators

Safety will be monitored by the following parameters: vital signs (systolic and diastolic blood pressure, respiratory rate and pulse rate), oxygen saturation of the blood using pulse oximetry, clinical laboratory parameters, and adverse event assessments for approximately 24 hours (20 to 36 hours) after Technegas inhalation. A physical examination will be obtained during screening and at the 24-hour follow-up safety assessment.

If a clinically significant change from baseline is observed, and it represents a worsening of a clinical condition for any safety parameter, the change will be considered an AE, it will be documented on the AE page of the CRF, and the investigator will continue to monitor the subject until the parameter returns to baseline levels or until the investigator judges that

follow-up is no longer necessary.

11.2.1 Clinical Laboratory Measurements

Subjects will have blood drawn during screening and at the 24-hour follow-up safety assessment to obtain clinical laboratory measurements. Blood samples will be sent for analysis by a central laboratory.

The following clinical chemistry measurements will be obtained: albumin, alkaline phosphatase, alanine aminotransferase (ALT), aspartate aminotransferase (AST), blood urea nitrogen (BUN), calcium, chloride, carbon dioxide (CO₂), serum creatinine, direct bilirubin, gamma-glutamyl transpeptidase (GGT), glucose, lactate dehydrogenase (LDH), serum phosphorus, potassium (K⁺), sodium (Na⁺), total bilirubin, total cholesterol, total protein, uric acid.

The following hematology measurements will be obtained: hemoglobin (Hgb), hematocrit (Hct), red blood cell count (RBC), mean corpuscular volume (MCV), mean corpuscular hemoglobin (MCH), mean corpuscular hemoglobin concentration (MCHC), red cell distribution width (RDW), mean platelet volume (MPV), white blood cell count (WBC), white blood cell differential, including lymphocytes, neutrophils, monocytes, eosinophils, and basophils.

The investigator will compare 24-hour post-Technegas measurements to baseline measurements and comment on any changes that are considered clinically significant. Attributability of any changes considered clinically significant will be assessed as follows:

- 1 = Attributable to disease; no follow-up required
- 2 = Possibly attributable to Technegas, FOLLOW-UP REQUIRED
- 3 = Apparent laboratory error
- 4 = Unevaluable; includes instances where baseline values not reported and instances where sample was hemolyzed

Any changes considered clinically significant and assessed as “2 = Possibly attributable to Technegas, FOLLOW-UP REQUIRED” will be documented on the AE page of the CRF.

All laboratory tests with clinically significant changes will be repeated at appropriate intervals following the procedure until the values return to baseline or until the investigator and the Medical Monitor agree that further follow-up is no longer clinically relevant.

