11.2.4 Oxygen Saturation of the Blood using Pulse Oximetry

Oxygen saturation of the blood using pulse oximetry will be collected within 30 minutes prior to the Xe-133 study. This will be considered the baseline measurement. Oxygen saturation will also be taken following completion of the Xe-133 imaging, but prior to Technegas imaging.

Oxygen saturation will be taken at approximately 10 minutes (\pm 5 minutes) prior to Technegas inhalation and within 15 minutes following completion of the Technegas imaging. Additional oxygen saturation will be taken during the 24-hour follow-up safety assessment.

The investigator will assess and comment if oxygen saturation falls below 90%.
Attributability of any changes below 90% will be assessed as follows:

- 1 = Attributable to disease; no follow-up required
- 2 = Attributable to Xe-133 procedure; no follow-up required
- 3 = Possibly attributable to Technegas, FOLLOW-UP REQUIRED

Any oxygen saturation measurements with clinically significant changes below 90% and possibly attributable to Technegas will be repeated at appropriate intervals following the procedure until the values return to baseline or until the investigator and the Medical Monitor agree that further follow-up is no longer clinically relevant.

Any changes considered clinically significant and assessed as “3 = Possibly attributable to Technegas, FOLLOW-UP REQUIRED” will be documented on the AE page of the CRF.

11.2.5 24-Hour Follow-Up Safety Assessment

Subjects will return to the clinical site for a 24-hour follow-up safety assessment, to occur within 20 to 36 hours following the Technegas procedure. Subjects will undergo a physical examination, a blood draw for clinical chemistry and hematology laboratory measurements, vital signs (systolic and diastolic blood pressure, pulse rate, respiratory rate), pulse oximetry, and adverse event and concomitant medication assessments. Adverse event follow-up safety assessment will conclude at this visit if none are noted.

Any changes that the investigator feels are clinically significant should be noted and the investigator will comment on whether the change can be attributed to Technegas. If clinically significant changes are noted, appropriate follow-up will be conducted by the investigator as long as deemed necessary.

Investigators will make every effort to obtain the 24-hour assessment, as agreed to by the subject prior to enrollment.

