11.3 Adverse Events

An AE is any untoward medical occurrence in a subject administered an investigational drug, which does not necessarily have a causal relationship with the treatment. An AE can be any unfavorable or unintended sign (e.g., an abnormal laboratory finding), symptom, or disease temporally associated with the use of the study drug, whether or not it is considered to be study drug related. This includes any newly occurring event or previous condition that has increased in severity or frequency since the administration of the drug.

All AEs, ascertained through subject interview, physical examination or other means will be recorded on the AE page of the CRF. Adverse events will be recorded beginning at the time the subject signs the informed consent. Any AEs recorded before Technegas inhalation will be considered a pre-treatment AE.

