11.3.6 Relationship to Study Drug

Relationship to study drug administration will be determined as follows:

None	No relationship between the experience and the drug; related to other etiologies such as concomitant medications or subject's clinical state.
Unlikely	The current state of knowledge indicates that a relationship is unlikely.
Possible	A reaction that follows a plausible temporal sequence from use of the drug and follows a known response pattern to the suspected drug. The reaction might have been produced by the subject's clinical state or other modes of therapy administered to the subject.
Probable	A reaction that follows a plausible temporal sequence from the use of the drug and follows a known response pattern to the suspected drug. The reaction cannot be reasonably explained by the known characteristics of the subject's clinical state or other modes of therapy administered to the subject.
Definite	A reaction that follows a plausible temporal sequence from use of a drug and follows a known response pattern to the suspected drug.

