11.4 Follow-up of Adverse Events

Subjects will return to the clinical site for a 24-hour follow-up safety assessment which will include an assessment of AEs. Any AE that is on-going at the time of the 24-hour follow-up assessment will be followed by the investigator until resolution or until the principal investigator and the Medical Monitor agree that further follow-up is no longer clinically relevant.

If subjects do not return for the 24 hour safety assessment, a follow-up telephone contact for AE resolution assessment must be documented on the CRF and in subject records, including

date, time and summary of conversation.

11.5 Procedures for Reporting AEs, SAEs and Suspected Unexpected Serious Adverse Reactions (SUSARs)

All AEs spontaneously reported by the subject and/or in response to an open question from study personnel or revealed by observation, physical examination or other diagnostic procedures will be recorded on the AE section of the CRF. Any clinically relevant deterioration in laboratory assessments or other clinical findings is considered an AE must be recorded on the AE section of the CRF.

All AEs will be noted and evaluated on the CRF with a full description of the nature, onset, duration, severity, attribution, and outcome of the event. All AEs will be coded using MedDRA. Any treatment used to alleviate the AE(s) will also be recorded.

Adverse event recording and reporting will conform to International Conference on Harmonisation (ICH) of Technical Requirements for Registration of Pharmaceuticals for Human Use Guidelines for Clinical Safety Data Management.

When possible, signs and symptoms indicating a common underlying pathology should be noted as one comprehensive event. All AEs should be recorded using standard medical terminology.

All SAEs that occur during the course of the study, as defined by the protocol, must be reported immediately by the investigator to the Medical Monitor by telephone or fax within 24 hours of the time the investigator first becomes aware of the SAE. Such preliminary reports should be followed with a detailed written description (within 5 days) which will include copies of hospital records and other documents when applicable.

All SAEs must be reported whether or not considered causally related to the study product. An SAE form will be provided to each clinical study site.

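### Protocol 11.2.1 and 11.2.4 attach the AE-page instruction to the possible-Technegas code alone, while 11.2, 11.3 and 11.5 record clinically significant worsening whatever its cause

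*Combined protocol and SAP*

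**What the plan says.** Two subsections of the protocol link the AE page to one attribution code.

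- **11.2.1 (laboratory).** Clinically significant changes receive one of four codes: disease, possible Technegas cause, laboratory error, or unevaluable. The recording sentence is "Any changes considered clinically significant and assessed as “2 = Possibly attributable to Technegas, FOLLOW-UP REQUIRED” will be documented on the AE page". The disease code reads "1 = Attributable to disease; no follow-up required".
- **11.2.4 (SpO2).** Falls below 90% receive one of three codes: disease, Xe-133 procedure, or possible Technegas cause. The recording sentence is "Any changes considered clinically significant and assessed as “3 = Possibly attributable to Technegas, FOLLOW-UP REQUIRED” will be documented on the AE page". The disease and Xe-133 codes carry the same no-follow-up label.

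The general rules have no such condition.

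- **11.2.** If any safety parameter shows a clinically significant change that is a worsening, "the change will be considered an AE, it will be documented on the AE page of the CRF".
- **11.3.** An AE is defined "whether or not it is considered to be study drug related", and all AEs go on the AE page.
- **11.5.** "Any clinically relevant deterioration in laboratory assessments or other clinical findings is considered an AE must be recorded".
- **11.3.6.** The relationship scale has a grade for unrelated events: "No relationship between the experience and the drug; related to other etiologies such as concomitant medications".

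The sister subsections 11.2.2 (physical examination) and 11.2.3 (vital signs) send clinically significant worsening to the AE page with no test of attribution.

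**The concern.** Site staff who code a laboratory change or a low saturation will probably have the parameter's own subsection in front of them. There they find an AE-page instruction for one code and none for the others. It is natural to read that as a filter, especially as 11.2.2 and 11.2.3 have no such condition.

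The usual order is to record the event first and grade its relationship afterwards, and 11.3.6 is built for that. A filter on attribution reverses the order. It also rests on a difficult judgement: the study is open-label, Xe-133 always comes first, and 6.2 accepts that the two agents may confound each other's effects on safety parameters.

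Incidence of treatment-emergent AEs is safety endpoint 1 in 13.8 and serves primary objective 2. Under 13.9, AEs are also summarised by relationship to treatment, and that table needs the unrelated events in order to be read correctly. According to the SAP Addendum (section 1), an interim safety report has already gone into the NDA.

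**Working it through.** The plan has no figure to reproduce here. The check compares the text code by code.

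| Parameter and code | AE-page instruction in its own subsection | Under 11.2, 11.3 and 11.5, if the worsening is genuine | Conflict |
|---|---|---|---|
| Laboratory 1, disease | none | record | yes |
| Laboratory 2, possible Technegas cause | record | record | no |
| Laboratory 3, laboratory error | none | not a real worsening | no |
| Laboratory 4, unevaluable | none | record only if a real deterioration lies behind it | only in that case |
| SpO2 1, disease | none | record | yes |
| SpO2 2, Xe-133 procedure | none | record | yes |
| SpO2 3, possible Technegas cause | record | record | no |

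The instruction is attached to 1 of 4 laboratory codes and 1 of 3 SpO2 codes. Three codes are exposed: laboratory 1, SpO2 1 and SpO2 2.

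**Which events reach the endpoint.** Under 11.3, "Any AEs recorded before Technegas inhalation will be considered a pre-treatment AE". SpO2 falls before Technegas inhalation therefore do not affect the treatment-emergent count. Only the two post-Technegas readings matter: within 15 minutes after imaging, and at the 24-hour visit.

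**What else would catch an omitted event.** Endpoint 3 in 13.8 counts clinically significant laboratory changes independently of the AE page. For SpO2, 13.8 names only change from baseline (endpoint 6), and 13.9 names it only among the continuous summaries. A post-Technegas fall coded 1 or 2 and not entered as an AE would show in listings, comments and mean changes, but in no incidence count that the protocol names.

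**Scale only.** SAP Addendum section 2 reports 225 enrolled and 16 withdrawn before Technegas, so 225 − 16 = 209 subjects, all with complete data. If k subjects have their only treatment-emergent event left off the AE page, incidence falls by k/209. The values of k are assumed:

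- k = 1: 1/209 = 0.48 percentage points
- k = 5: 5/209 = 2.39 percentage points
- k = 10: 10/209 = 4.78 percentage points

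**Ceiling on the matching exercise.** 11.2.1 lists 20 chemistry and 14 haematology tests (9 indices plus 5 differential components), so 34 × 209 = 7,106 laboratory comparisons. There are 2 × 209 = 418 post-Technegas SpO2 readings. These count measurements, not events; only readings that were given a code need checking.

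**Follow-up wording.** In 11.2.1 the disease code says no follow-up is needed, yet the same section has all laboratory tests with clinically significant changes repeated. The SpO2 disease and Xe-133 codes carry the same label, while 11.2 continues monitoring of any worsening parameter and 11.4 follows ongoing AEs.

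**The case against.** The best defence is that the passages can be read together. 11.2.1 and 11.2.4 sit under 11.2, which already covers every safety parameter, and neither sentence says that other codes stay off the AE page. Both speak of changes rather than worsening, so they can be taken as adding to 11.2. 11.2.5 also has clinically significant changes at the 24-hour visit noted, with a comment on attribution to Technegas. This stands: there is no explicit prohibition, and harm requires a site to follow the narrow sentence and overlook three general rules.

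Safeguards exist. 14.4 targets clinical safety, AEs and laboratory assessment for verification, and under 15.1 the monitor assesses whether all AEs were appropriately reported. The Monitoring Plan and Data Management Plan were not supplied and may already contain a cross-check of codes against the AE page. The frequency summaries named in 13.9 are not an exhaustive list, and SAP Version 2, also not supplied, may include an SpO2 incidence table. These points make the fix conditional. They do not remove the problem, because a monitor working from the protocol sees the same two instructions.

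AE incidence is summarised descriptively, with no hypothesis test, and no efficacy decision depends on it. That limits the importance of the point. On follow-up, 11.2 lets the investigator judge that monitoring is no longer necessary, which softens the conflict but does not resolve it.

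A reader might go further and infer that the protocol forbids recording unrelated events, or that AEs in the interim safety report were undercounted. The documents support neither: no sentence forbids it, and nothing shows how sites read the text or that any event was missed.

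**Conclusion.** The site instructions are inconsistent, and the inconsistency can affect a named safety endpoint. If a site treats the code-specific sentence as a filter, treatment-emergent AE incidence falls and the relationship summary loses unrelated events, which tilts it towards related ones. If sites follow 11.2, 11.3 and 11.5 as well, nothing is lost.

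The size cannot be estimated. The figure of 0.48 percentage points per affected subject is arithmetic on the 209 subjects at the addendum. It is not a forecast, and the final number dosed is not known.

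Laboratory data are partly protected by endpoint 3. SpO2 is the weaker spot on the protocol text, subject to what SAP Version 2 contains. The primary efficacy analysis is not affected.

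**What to change.** **(a) Match codes to the AE page.** Unless the Monitoring Plan or Data Management Plan already provides for it, and provided the codes are on the CRF, match every laboratory code 1 entry and every post-Technegas SpO2 code 1 or 2 entry to the AE page before the safety tables are produced. Cover all dosed subjects, including those in the interim safety report. Query any unmatched clinically significant worsening.

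**(b) Reconcile the recording text if enrolment resumes.** Bring the AE-page sentences in 11.2.1 and 11.2.4 into line with 11.2, 11.3 and 11.5, so that AE recording does not depend on attribution and cause is held in the 11.3.6 relationship field.

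**(c) Add an SpO2 table.** Unless SAP Version 2 already has one, tabulate subjects with post-Technegas SpO2 below 90% by attribution code. Separate those at or above 90% at baseline from those already below it: no exclusion criterion bars low saturation at entry, so a low reading is not always a worsening.

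**(d) Reconcile the follow-up text.** The sponsor must reconcile the no-follow-up labels (laboratory code 1, SpO2 codes 1 and 2) with the repeat-test sentence in 11.2.1 and the continued monitoring in 11.2 and 11.4. This includes any follow-up that AE entry under (b) would trigger. No follow-up rule is proposed here.

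**Cost.** Item (a) is a listing match with site queries, and (c) uses data already collected. Item (b) is a protocol amendment that needs submission to FDA and the IRB/IEC and approval under 17.2; if the trial stops at the interim, it falls away. The downside is some query work and a possibly higher reported AE count.
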